14 In 2017, ATSDR published a feasibility assessment of possible future drinking water epidemiological 15 studies at the Pease International Tradeport, Portsmouth, New Hampshire (ATSDR 2017a). Drinking water 16 supply wells serving the Pease Tradeport were contaminated with PFAS from the use of AFFF at the former 17 Pease Air Force Base. As part of this feasibility assessment, ATSDR reviewed the available information on 18 the Pease Tradeport population and exposures (e.g., population size and demographics, PFAS 19 biomonitoring results, and drinking water data) as well as conducted sample size calculations. The ATSDR 20 feasibility assessment concluded that there was a need for additional epidemiological research on the 21 health effects of PFAS exposures to address several research gaps and issues: (1) the small number of studies for some health endpoints, (2) the inconsistency of findings across studies for some health 22 23 endpoints, (3) the lack of drinking water studies other than the C8 studies, and (4) the need to conduct studies that evaluate PFHxS and PFNA as well as other PFAS chemicals in addition to PFOA and PFOS 24 25 (ATSDR 2017a).

In addition, ATSDR determined that cross-sectional epidemiological studies of children and adults at one
site (e.g., at the Pease Tradeport) were feasible for some health endpoints (e.g., lipids, kidney function),
but the size of the populations would be insufficient for other important health endpoints (e.g., thyroid,
liver and immune function, autoimmune diseases). Therefore, the feasibility assessment concluded that:
(1) a multi-site PFAS study of children and adults was necessary, (2) the study should be cross-sectional
and involve separate evaluations of children (ages 4-17) and adults (ages ≥18), and (3) the study should

focus on communities impacted by PFAS-contaminated public drinking water supply wells and/or private wells. A cross-sectional study design was chosen because this design is especially suitable for assessing effect biomarkers and the prevalences of nonfatal diseases, in particular, diseases with no clear point of onset (Checkoway 2004). Additionally, the cross-sectional design can generate data for hypotheses that can be tested in subsequent longitudinal studies.

6

7 1.1.3 Summary of Study Goals

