The main goal of the cross-sectional multi-site study is to evaluate associations between measured and historically reconstructed serum levels of PFAS including PFOA, PFOS, and PFHxS (see Section 3.10), and selected health outcomes as described below and detailed in study hypotheses (see Section 2.5.2). The study will attempt to recruit at least 2,000 children and 6,000 adults (equally of both sexes for both children and adults) from communities exposed to PFAS-contaminated drinking water. The criteria for selecting study sites are detailed in Section 2.3 and would include:

- 14 1. Documented past or present PFAS drinking water concentrations at the tap,
- 15 2. The magnitude of past or present PFAS concentrations at the tap,
- 16 3. Size of the population exposed,
- 17 4. Amount of information available on the contaminated drinking water system or private wells, and
- 18 5. If biomonitoring for PFAS has previously occurred at the site.

Possible candidate sites include communities whose drinking water was impacted by AFFF use at military bases or by industrial PFAS emissions. Site selection process will consider the levels of PFAS drinking water concentrations at a site. The aim will be to select sites so that a wide range in PFAS exposures levels are included in the study in order to enable the evaluation of exposure-response trends including effects at the lower range of exposures.

For those sites with complex drinking water systems (e.g., where individual supply wells serve particular areas of the distribution system, or when there is uncertainty concerning which areas in the distribution system received contaminated water) or sites with groundwater contamination affecting private wells where there is uncertainty concerning which wells are contaminated, it may be necessary to use modeling methods (e.g., ground water contaminant fate and transport models, water system distribution system
models) to identify the areas with contaminated drinking water. A targeted PFAS biomonitoring approach
is essential to confirm results from groundwater and/or distribution system modeling approaches.
Modeling may also be necessary to determine the period when the drinking water was contaminated and
to historically reconstruct PFAS contaminant concentrations during this period (Shin 2011).

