The C8 studies used PBPK modeling to estimate cumulative serum levels of PFOA and PFOS (Shin 2011). 16 17 The model incorporated information from the historical reconstruction of PFAS concentrations in the drinking water serving the C8 areas, questionnaire data on each participant's water consumption, and the 18 19 serum levels of PFOA and PFOS obtained from study participants. A recent effort to reconstruct historical 20 exposures worked well for PFOA and PFOS; the model for PFHxS serum levels using biomonitoring data in 21 the US and Australia did not work as expected (Gomis 2017). Low environmental concentrations, lack of 22 decline in older population, possible ongoing exposure in children/younger adults, and scarcity of time-23 trend data in consumer products were cited as reason for poor prediction characteristics of PFHxS models 24 (Gomis 2017). However, if there are high correlations in serum levels between PFHxS and PFOS and/or 25 PFOA, then it may be possible to estimate cumulative PFHxS serum levels based on the historical estimates 26 for serum PFOS and/or PFOA.

Recently, an online serum PFOA calculator for adults became available using a modified one-compartment
 exponential decay model to estimate PFOA serum levels from PFOA concentrations in drinking water
 (Bartell 2017). Developing a similar calculation for serum PFOS is possible. The studies of children and

adults by ATSDR and recipients will explore this approach to estimate serum PFOA, PFOS, PFHxS and PFNA
 levels and make comparisons with serum levels from the blood specimens obtained in this study (and if
 available, previous PFAS serum measurements). The recipient may consider the use of a one compartment PBPK model similar to one used by Shin (2011) and Avanasi (2016), and also used as the
 basis for a recent PFOA serum calculator (Bartell SM 2017).

A number of improvements in PBPK modeling approaches, especially as related to multi-compartment
models, have been developed recently and the recipient should take those into consideration (Loccisano
2013, Fabrega 2014, 2016; Verner 2015, 2016).

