 the source via ground water, then the recipient should seek information on the extent of the
 contamination plume from the state environmental agency, EPA, and/or the industrial facility.

If the contaminated drinking water is from a municipal system, then the characteristics of the distribution system will be obtained from the water purveyor. If supply wells are used, then the recipient will request historical and current information on these wells including monthly or daily production logs and dates of operation. If a surface water source is used or if water is purchased from another purveyor, then the recipient will request information about this source.

10 The recipient will also request the results of all relevant PFAS sampling: in the surface water near the 11 drinking water intakes, in the distribution system, in the supply wells and nearby monitoring wells, in 12 purchased water from other water purveyors, and in the private wells in the study area.

13

14 **3.10 Statistical Analyses**

15 ATSDR staff will perform statistical analyses with the participation of the recipients using SAS, R and STATA 16 on the combined multi-site study dataset. ATSDR staff may also use SPSS for data management. ATSDR 17 staff will calculate descriptive statistics (including means, geometric means, medians, standard deviations, 18 and percentiles) to identify the presence and distribution of PFAS and effect biomarker analytes. Statistical 19 methods will include multiple linear regression of continuous (untransformed and natural log transformed) effect biomarkers on continuous (untransformed and natural log transformed) PFAS serum 20 21 levels and categorized PFAS serum levels, and logistic regression of categorized effect biomarkers (e.g., 22 hypercholesterolemia) or disease prevalence on continuous (untransformed and natural log transformed) 23 and categorical PFAS serum levels. ATSDR staff will use restricted cubic spline methods (or generalized 24 additive models using cubic regression splines) for linear and logistic regression to obtain flexible, 25 smoothed exposure-response curves. To identify risk factors that may act as confounders for a particular health outcome, the analysis will implement a "10% change in the estimate" rule (Maldonado 1993). 26

Primary analyses will focus on estimated cumulative PFAS serum levels. Supplemental analyses will
evaluate PFAS serum levels in the blood specimens obtained in the study as well as estimated maximum

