and average PFAS serum levels. The primary analyses will evaluate each PFAS chemical separately; sum

of PFAS measures may also be considered. Statistical analyses using prevalent cases in a cohort design 1 2 which takes into consideration the times of diagnosis will also be conducted. ATSDR will explore the use 3 of methods for evaluating multi-pollutant mixtures, such as the hierarchical Bayesian model, to analyze 4 the effects of exposures to the PFAS mixtures. ATSDR will use quantitative methods to assess the impact 5 of possible selection bias and possible confounding due to unmeasured risk factors (Lash 2009). There 6 are several caveats and recommendations in conducting analyses of mixtures to determine the optimal 7 method that avoids amplifying bias due to confounding (Weisskopf et al 2018). For the bias analyses, ATSDR will identify "negative control" diseases with no known association with PFAS exposures (Lipsitch 8 9 2010). ATSDR conducted a literature search to identify these negative control diseases and included them 10 in the questionnaire.

ATSDR will interpret the findings from this study based on the magnitude of the effect estimates (e.g., the linear regression coefficient for continuous outcomes or the odds ratio for categorical outcomes) of the exposure-response relationship, consistency with findings from other studies, and the possible sources of bias (Rothman 2014). The analyses will construct confidence intervals to indicate the level of precision (or uncertainty) in the effect estimates.

The studies will use statistical significance testing to interpret findings but will not use it as a sole factor in determining scientific and public health significance (Rothman et al. 2008, 2010; Stang et al. 2010). A finding that fails to achieve statistical significance can still provide evidence for a causal association, and a finding that achieves statistical significance can lack any such significance (Porta 2014).

20 4. RESULTS REPORTING

21 4.1 Notification of Individual Results

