Generally, ATSDR will publish study results only as group data analyses in peer-reviewed scientific journals or government reports. If individual data are presented, those will not be linked to participants' identities. In the event that some other exceptional characteristics would enable personal identification, those would be masked or modified as needed to protect individual privacy. ATSDR will use manuscripts published in peer-reviewed scientific journals and presentations at major scientific meetings to inform the scientific community about the results of the Multi-site studies.

24 **5. STRENGTHS AND LIMITATIONS**

Cross-sectional studies are especially suitable for assessing effect biomarkers and the prevalences of nonfatal diseases, in particular, diseases with no clear point of onset (Checkoway 2004). However, if the cross-sectional study concurrently measures the exposure and the outcome (i.e., the disease or effect biomarker), it might be difficult to determine whether the exposure caused the outcome or whether the

outcome influenced the measured exposure level (Flanders 1992, 2016). For example, as discussed above, 1 2 the concurrent measurement of serum PFAS levels and kidney function biomarkers might raise the 3 question of "reverse causation" because kidney function can affect the levels of PFAS in serum. One approach to minimize the problem of reverse causation or possible confounding due to health outcomes 4 5 that affect PFAS serum levels is by estimating exposures based on the historical reconstruction modeling 6 of serum PFAS levels. In addition, it might be possible to estimate exposures during critical vulnerable 7 periods (e.g., in utero exposure) through the modeling of historical serum PFAS levels. However, the 8 modeling of historical PFAS serum levels is subject to uncertainties and data limitations, and published 9 methods currently are available only to model serum levels of PFOA and PFOS.

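### PFHxS derived from PFOS and/or PFOA should be barred as a primary exposure: Section 3.9 leaves that route open, and it would carry no PFHxS-specific information

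*Protocol*

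**What the plan says.** Section 3.10 sets the primary exposure: "Primary analyses will focus on estimated cumulative PFAS serum levels". It adds that "The primary analyses will evaluate each PFAS chemical separately". Measured serum is supplemental; those analyses will "evaluate PFAS serum levels in the blood specimens obtained in the study as well as estimated maximum" and average levels.

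PFHxS is central to the study. The main goal in Section 1.1.3 refers to "historically reconstructed serum levels of PFAS including PFOA, PFOS, and PFHxS", and Section 1.1.2 lists as a research gap "the need to conduct studies that evaluate PFHxS and PFNA".

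On feasibility, Section 5 says that published "methods currently are available only to model serum levels of PFOA and PFOS". Section 3.9 reports that a recent reconstruction worked for PFOA and PFOS but that its PFHxS model fell short. It then offers two ways forward for PFHxS:

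- If serum PFHxS correlates strongly with PFOS and/or PFOA, "then it may be possible to estimate cumulative PFHxS serum levels based on the historical estimates" for those two chemicals.
- A one-compartment calculation is to be tried for PFOA, PFOS, PFHxS and PFNA, and compared with serum measured in the study and with earlier results where available.

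Section 3.9 also lists the participant's own measured serum and reconstructed water concentrations among the inputs to the cumulative estimates.

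**The concern.** Nothing in Sections 3.9 or 3.10 keeps the first route out of the primary analysis. A PFHxS value computed only from PFOS and PFOA is a function of those two chemicals. Two analyses presented as separate would then rest on the same information, and a PFOS or PFOA effect could be reported as a primary PFHxS finding even if PFHxS had none. This would happen for the chemical on which the study is meant to add evidence. The gate that the protocol sets, a strong correlation between serum levels, does not protect against it: a strong correlation makes the proxy look acceptable without adding anything specific to PFHxS.

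**Working it through.** **1. The plan's own PFHxS-based sizes.** Inputs are from Table 1 and Attachments 3a and 3b. With n per stratum = 2·SD²·(1.960 + 0.8416)²/Δ², where the squared term is 7.849:

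- IGF-1 (SD 52.6, Δ 17.3): 2 × 52.6² × 7.849 / 17.3² = 145.1, so 146 (stated 146).
- TSH (SD 0.82, Δ 0.12): 733 (stated 733).
- TT4 (SD 1.04, Δ 0.06): 4,716.3 (stated 4,716).

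These reproduce. They say nothing on how PFHxS is estimated, which is the question here.

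**2. Proxy from PFOS alone.** Let ln H* = a + b·ln S, with S for PFOS and H* for derived PFHxS. Regressing an outcome on ln H* divides both the PFOS slope and its standard error by b, so t and p do not change. A simulation with n = 6,000 and an outcome that depends only on PFOS (slope 0.1 per SD) confirms this:

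| b (assumed) | PFOS slope | Derived PFHxS slope | t, PFOS | t, derived PFHxS | Same quartile |
|---|---|---|---|---|---|
| 0.6 | 0.1189 | 0.1981 | 9.2744 | 9.2744 | 100% |
| 0.8 | 0.0940 | 0.1175 | 7.2479 | 7.2479 | 100% |
| 0.9 | 0.1098 | 0.1220 | 8.4212 | 8.4212 | 100% |

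Any increasing conversion keeps the ranks, so the quartile analyses coincide even if the conversion is not log-linear.

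**3. Proxy from PFOS and PFOA.** Take H* = 0.5·S + 0.3·O on the log scale, with O for PFOA and a PFOS–PFOA correlation of 0.6 (illustrative values). Writing O = 0.6·S + 0.8·E gives H* = 0.68·S + 0.24·E. Its correlation with PFOS is 0.68/√(0.68² + 0.24²) = 0.94. Simulated quartile agreement with PFOS is 72–73%. A design matrix with an intercept, S, O and H* has rank 3 of 4. The mixture methods in Section 3.10 therefore cannot separate derived PFHxS from its sources using the data.

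**4. Contrast: PFHxS estimated on its own.** With true PFOS–PFHxS correlations of 0.6, 0.8 and 0.9 and error SD 0.5 (all assumed), quartile agreement with PFOS is 40%, 49% and 55%. When both enter the model, t for PFOS is 7.20, 5.55 and 5.38, and t for PFHxS is 1.11, −0.72 and −0.52. A pure PFOS effect then stays with PFOS. The problem belongs to the proxy route only.

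**5. Half-lives.** Section 3.2.1 gives about 3 years for PFOS and about 5 for PFHxS, and eligibility allows up to 15 years since last exposure. For the water-derived part, the PFHxS/PFOS ratio after t years, relative to the end of exposure, is 2^(t/3 − t/5):

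- t = 0: 1.00
- t = 5: 1.59
- t = 10: 2.52
- t = 15: 2^(5 − 3) = 4.00

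Section 3.2.1 also mentions half-lives of 5 to 8 years from another source without tying them to compounds. Assigning 5 to PFOS and 8 to PFHxS (an assumption) gives 2^(15/5 − 15/8) = 2.18 at 15 years. A conversion fitted to current serum pools participants across this range.

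**6. Power, if PFHxS is the true cause.** With a proxy correlated r with true PFHxS, the required size rises roughly as n/r² (r is assumed; the protocol gives none). IGF-1's 146 per stratum becomes 162 at r = 0.95, 229 at r = 0.8 and 406 at r = 0.6.

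**The case against.** The strongest reply is that the proxy is an option and not the plan. It is doubly hedged: it needs strong correlations, and even then is only called possible. The next paragraph of Section 3.9 has a PFHxS-specific calculation tried and compared with study serum, and recipients are pointed to newer multi-compartment models. The reconstruction that fell short used US and Australian biomonitoring data. Two of the reasons given, low environmental levels and sparse consumer-product data, do not carry over directly to sites with measured water contamination, such as the 0.96 µg/L of PFHxS cited for Pease in Section 2.2. Modelled serum was made primary for a good reason, to limit reverse causation (Sections 1.1.3 and 5). Measured PFHxS is still analysed, so a divergence would show. Acceptance criteria for models may also sit in a statistical analysis plan that is not shown.

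Much of this stands. A reader might infer that the protocol will derive PFHxS from PFOS, so that its PFHxS result is bound to be a PFOS result under another name. The text does not support that, because a separate route is written in. Nor does it support a mismatch with the hypotheses and sample sizes: Section 1.1.3 covers measured and reconstructed serum, Section 3.3 allows cumulative categories, and Attachment 3b works an example from cumulative PFOA. PFNA shares the lack of published models, but no proxy is proposed for it.

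None of this removes the point. The proxy is named in the protocol, it is not excluded from the primary analysis, and it cannot do what a primary PFHxS exposure must do.

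**Conclusion.** The point holds in conditional form. The primary metric for PFHxS rests on a type of model that the protocol says has not been published, and one of its two named routes would yield a PFHxS analysis with no PFHxS-specific content. Equality with the PFOS analysis is exact only for a log-linear conversion from PFOS alone (or, for quartiles, any increasing one). With PFOA added the result is a composite, inseparable when the conversion is linear on the scale used in the model. The fourfold shift is an upper figure: it applies to the water-derived part of serum, at 15 years, with half-lives of 3 and 5 years. The correlations, weights and error SD are assumptions that illustrate the mechanism. If the participant's own measured PFHxS enters the estimate, or a PFHxS model passes its check against serum, the criticism does not apply.

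**What to change.** In Sections 3.9 and 3.10, state that cumulative PFHxS estimated from PFOS and/or PFOA will not serve as a primary exposure. It may appear only as a labelled sensitivity analysis that is not interpreted as a PFHxS effect. State that the primary PFHxS exposure is a PFHxS-specific model checked against measured serum. If no such model is obtained, report the measured-serum PFHxS analysis as the main PFHxS result, with the reverse-causation caveat beside it.

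The cost is a few sentences; the measured-serum analysis is already planned and needs no new data. The downside is that, if the PFHxS model fails, the main PFHxS result is open to reverse causation and its primary metric differs from that of PFOA and PFOS. For that reason measured serum is proposed as the fallback and not as the outright primary metric.

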	Sh-DEOA - serum branched isomer	Yes	Serum	1 ml reserve (for future PFAS	6-11:	< LOD - 0.230
	SD-FT OA - Sei um brancheu isomer				12-19:	< LOD – 0.200
Contact: [name]					20+:	< LOD – 0.200
[name]					3-5:	3.41 - 8.82
	perfluorooctane sulfonic acid, (PFOS)‡				6-11: 12 10:	4.02 - 12.4
				analyse	20+·	5.00 - 9.30 5.60 - 19.5
				s) .	3-5:	2.11 - 6.19
					6-11:	2.65 - 8.41
	n-PFOS – linear isomer				12-19:	2.70 - 7.10
					20+:	3.70 – 15.1
					3-5:	1.00 - 3.60
	Sm-PEOS – serum branched				6-11:	1.41 – 4.25
	Sin 1105 Schull branchea				12-19:	1.00 - 2.30
					20+:	1.60 – 5.30

Dischamical analy	tical .		مامالم	مهدا بمانيا العمد		- laharatariaa	reference levels	ronortin.		المعنسالم	ممالمانيه	اممنا مستعتمه	valua
Diochemical analy	ylicai	ριαπ πι	CIIIIUIEII	anu auuits.	periorining	giabulatulies	, I CICI CIICE IEVEIS	, reporting	s i aliges	, ciinicai j	guiueiiiies	, and critical	values

Limit of detection (LOD, see Data Analysis section) for Survey year 13-14 is 0.1. < LOD means less than the limit of detection, which may vary for some chemicals by year and by individual sample.

¹CDC. 2018. 2013-2014 NHANES 50th to 95th percentiles among children 12-19 years and adults 20+ years old from the Fourth National Report on Human Exposure to Environmental Chemicals, Updated Tables, March 2018. Accessed April 13, 2018 at (https://www.cdc.gov/exposurereport/pdf/FourthReport_UpdatedTables_Volume1_Mar2018.pdf). ‡ See Calculation of PFOS and PFOA as the Sum of Isomers for additional information in March 2018 Updated Tables.

Laboratory and Contact	Analyte		Matrix	Volume	NHANES ¹ (μg/L) 2013 - 2014	
Children and Adults			-	-		
	Per- and Poly-fluoroalkyl Substances (PFAS) (continued)				Age Group (years):	50 th to 95 th %
					3-5:	0.740 - 1.62
	perfluorobeyane sulfonic acid (PEHvS)				6-11:	0.850 - 4.14
	periodionexane suitonic acid (FTTXS)				12-19:	1.10 - 6.30
					20+:	1.40 – 5.50
					3-5:	< LOD - 0.110
	perfluorooctane sulfonamide (PEOSA)				6-11:	< LOD - < LOD
NCEH/Division of Laboratory Sciences*					12-19:	n/a [‡]
				1 ml (for all PFAS); 1 ml reserve (for future PFAS	20+:	n/a ‡
	2-(N-methyl-perfluorooctane sulfonamido) acetic acid (Me-PFOSAA)				3-5:	0.110 - 1.02
		Yes	Serum		6-11:	0.110 - 0.940
					12-19:	0.100 - 0.600
Contact: [name]					20+:	< LOD – 0.600
[name]	2-(N-ethyl-perfluorooctane sulfonamido) acetic acid (Et-PFOSAA)				3-5:	< LOD - < LOD
					6-11:	< LOD - < LOD
	(, p,,,,,,			analyses)	12-19:	n/a ⁺
					20+:	n/a †
					3-5:	< LOD - < LOD
	perfluorobutane sulfonic acid (PFBS)				6-11:	< LOD – 0.130
					12-19:	< LOD - < LOD
					20+:	< LOD - < LOD
	perfluoroheptanoic acid (PFHpA)				3-5:	< LOD - 0.310
					6-11:	< LOD – 0.170
					12-19:	< LOD – 0.200
					20+:	< LOD – 0.100

Limit of detection (LOD, see Data Analysis section) for Survey year 13-14 is 0.1. < LOD means less than the limit of detection, which may vary for some chemicals by year and by individual sample. ‡ Not measured after Survey Years 2011-2012.

¹CDC. 2018. 2013-2014 NHANES 50th to 95th percentiles among children 12-19 years and adults 20+ years old from the Fourth National Report on Human Exposure to Environmental Chemicals, Updated Tables, March 2018. Accessed April 13, 2018 at (https://www.cdc.gov/exposurereport/pdf/FourthReport_UpdatedTables_Volume1_Mar2018.pdf).
Laboratory and Contact	Analyte	* CLIA Cert.	Matrix	Volume	NHANES ¹ (μg/L)
Children and Adults		l	L	L	2013 - 2014
Children und Addits	Per- and Poly-fluoroalkyl Substances (PEAS) (continued)		[[Age Group (years): 50 th to 95 th %
NCEH/Division of Laboratory Sciences* Contact: [name]	perfluorononanoic acid (PFNA)				3-5: 0.620 - 3.49 6-11: 0.750 - 3.19 12-19: 0.500 - 2.00
	perfluorodecanoic acid (PFDA)	Yes	Serum	1 ml (for all PFAS); 1 ml reserve (for future PFAS analyses)	3-5: 0.100 - 0.370 6-11: < LOD - 0.350
	perfluoroundecanoic acid (PFUnDA)				3-5: < LOD - 0.370 6-11: < LOD - 0.250 12-19: < LOD - 0.200 20+: < LOD - 0.500
	perfluorododecanoic acid (PFDoA)				3-5: < LOD - < LOD 6-11: < LOD - < LOD 12-19: < LOD - 0.200 20+: < LOD - 0.200
Laboratory and Contact	Proposed Biospecimen Bank for Future Analytes	* CLIA Cert.	Matrix	Volume	NHANES ^{τΒD} (μg/L) 20xx – 20xx
Children and Adults		-	-	-	
NCEH/Division of Laboratory Sciences* Contact: [name]	 Per- and Poly-fluoroalkyl Substances (PFAS) To be determined (TBD) when analytical methods are developed (Including but not limited to the following 18 analytes: PFOA [n-PFOA;, Sb-PFOA], PFOA [n-PFOS, Sm-PFOS], PFHxS, PFBS, PFHpA, PFNA, PFDA, PFUnDA, PFPrS, PFHpS, PFBA, PFPeA, PFHxA, HFPO-DA (GenX), DONA, 9CI-PF3ONS) 	Yes	Spot Urine (morning void)	1 ml (for PFAS); 15 ml for creatinin e/or specific	Age Group: 50 th to 95 th % 3-5: TBD 6-11: TBD 12-19: TBD 20+: TBD
	Creatinine (for urinary creatinine correction; may be contracted)			gravity)	TBD

Limit of detection (LOD, see Data Analysis section) for Survey year 13-14 is 0.1. < LOD means less than the limit of detection, which may vary for some chemicals by year and by individual sample. ‡ Not measured after Survey Years 2011-2012.

¹CDC. 2018. 2013-2014 NHANES 50th to 95th percentiles among children 12-19 years and adults 20+ years old from the Fourth National Report on Human Exposure to Environmental Chemicals, Updated Tables, March 2018. Accessed April 13, 2018 at (https://www.cdc.gov/exposurereport/pdf/FourthReport_UpdatedTables_Volume1_Mar2018.pdf).

